5.2.5. M48 (Calendar month ± 14 days)

Visit M48 is the last visit in this study before entering the long-term follow-up study ABX464-108. If the patient is not eligible to enter this ABX464-108 study, she/he will perform the End of Study Visit (EoS) 4 weeks after last study drug intake.

The following examinations/procedures should be performed:

- Physical examination and vital signs;
- Body weight;
- Hematology and Biochemistry including blood pregnancy test for all women of childbearing potential and NT-proBNP;
- Faecal calprotectin dosage;
- 12 leads ECG;
- Blood sampling for miR-124 expression
- Partial Mayo Score;
- Total mayo score;
- Adverse Events and Concomitant Medications reporting;
- Sigmoidoscopy, mandatory;
- Echocardiography
- Schedule the EoS visit (if patient doesn't enter the study ABX464-108)

Nota bene:

- **The last treatment intake in study ABX464-102 should be the day before this visit M48.**
- **The local reading result of sigmoidoscopy need to be available on M48 visit to check eligibility to enter study ABX464-108.** The sigmoidoscopy can be performed within 14 days before the visit but not after the visit. If the sigmoidoscopy results (local reading) are not available on M48, the patient will be considered not eligible to enter the ABX464-108 study and will performed the end of study visit 28 days (+4 days) after M48.

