5.2.6. End of Study Visits

This EoS visit should be performed 28 days (+4 days) after the last study treatment dosing, or if a subject meets a discontinuation criterion before. From the last dosing day, subjects will be treated according to standard of care.

Following examinations/procedures should be performed:

- Physical examination and vital signs;
- Body weight;
- Hematology and Biochemistry including blood pregnancy test for all women of childbearing potential and NT-proBNP;
- Partial Mayo Score;
- 12 leads ECG;
- Faecal calprotectin dosage;
- Adverse Events and Concomitant Medications reporting.

NB: In case of premature discontinuation occurring during the treatment phase the above examinations should be performed as an End of Study Visit 4 weeks after treatment interruption.

After the end of study visit, patients will be treated according to the local standard of care.

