7. SUBJECT COMPLETION AND WITHDRAWAL

7.1. Subject Completion

Treatment duration with ABX464 is 48 months or earlier if one study discontinuation criterion is met (defined below).

The subjects exiting the study must perform the Follow-up and End of Study (EoS) visits 4 weeks after last study drug intake. They will be then treated according to the standard of care upon study treatment interruption.

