7.2. Study discontinuation criteria

Subjects who are not found eligible or not willing to enter the ABX464-108 study are not considered as prematurely discontinued as they have completed the scheduled treatment of ABX464-102 study.

A subject can be withdrawn at any time from the study for the following reasons:

Subject's study discontinuation could occur for the following reasons:

- Investigator's decision;
- An Adverse Event or an intercurrent condition that preclude continuation of treatment;
 - specifically, an increase $\geq 3.0 \times$ ULN in liver transaminases (AST/SGOT and/or ALT/SGPT) or an increase $\geq 2.0 \times$ ULN in Alkaline phosphatase or in total bilirubin requires close observation with repeating liver enzymes and serum bilirubin tests two times weekly and clinical investigation to understand the etiology of this elevation. Frequency of retesting can decrease to once a month if abnormality stabilizes after the initial two weeks of follow-up and if the patient is asymptomatic. Discontinuation of the study treatment should occur if:
 - ALT or AST $> 8 \times$ ULN
 - ALT or AST $> 5 \times$ ULN for more than 2 weeks
 - ALT or AST $> 3 \times$ ULN and total bilirubin $> 2 \times$ ULN or INR > 1.5
 - ALT or AST $> 3 \times$ ULN with appearance of fatigue, nausea, vomiting, right upper quadrant pain or tenderness, fever, rash, and/or eosinophilia ($> 5\%$);
 - Severe (grade 3 or higher) infection, a severe (grade 3 or higher) opportunistic infection, or sepsis;
 - Any cardiac AESI or condition diagnosed during the course of the study and assessed by the clinical adjudication committee as changing the risk/benefit balance for the subject;
 - New onset of acute pancreatitis;
 - Malignancies (including non-melanoma skin cancers);
 - Any relevant toxicity or negative change in the risk/benefit assessment leading to an unacceptable risk for the subject or any data deriving from other clinical trials or toxicological studies which negatively influence the risk/benefit assessment. This may be applicable but is not limited to the following cases: occurrence of AEs which character, severity or frequency is new in comparison to the existing risk profile, or clinically significant abnormal laboratory results, including new onset anemia (defined as a hemoglobin decrease > 2 g/dL from baseline or hemoglobin < 8 g/dL

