7.3. Study Discontinuation

All subjects, regardless of the completion or premature discontinuation, should perform the Follow-up and End of Study Visits according to the study flow-chart.

8. ADVERSE EVENTS (AE), ADVERSE EVENT OF SPECIAL INTEREST (AESI) AND SERIOUS ADVERSE EVENTS (SAE)

The investigator is responsible for the detection and documentation of events meeting the criteria and definition of an AE, AESI or serious adverse event (SAE). During the study, in case of a safety evaluation, the investigator or site staff will be responsible for reporting AEs, AESIs and SAEs, as detailed in this section of the protocol.

During the screening period, only adverse event related to the screening procedures will be collected.

Any disease progression will not be reported in the eCRF as an adverse event, but will be documented in the efficacy section.

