8.4.2. Pregnancy report

Subjects who become pregnant at any time will be immediately withdrawn from participation in the study. All appropriate withdrawal assessments may be performed at the discretion of the investigator.

The investigator will collect pregnancy information on any woman subject or partner of a male subject, who becomes pregnant and their partner while participating in this study. The investigator will record pregnancy information on a specific pregnancy notification form and submit it to IntuVigilance Limited (see contact details in section 8.4) within 24 hours after knowledge of a subject's or partner's pregnancy. The subject or partner will also be followed to determine the outcome of the pregnancy, be it full-term or prematurely terminated. Information on the status of the mother and child will be forwarded to ABIVAX or its designee. Follow-up will normally end 6 to 8 weeks following the estimated delivery date but could last up to one year after the delivery.

While pregnancy itself is not considered to be an AE or SAE, any pregnancy complication or elective termination of a pregnancy for medical reasons will be recorded as an SAE. A spontaneous abortion is always considered to be an SAE and will be reported as such.

The time period for collecting pregnancy information is identical to the time period for collecting AEs, as stated in Section 8.5, Time Period, Frequency, and Method of Detecting AEs and SAEs. Pregnancy information is collected from the signing of Pregnancy Follow up Inform Consent or Pregnant Partner Informed Consent to the end of the pregnancy follow-up.

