| Worsening of UC                  | xx (xx.x%)   | xx (xx.x%)                                     | xx (xx.x%)      |
| Major protocol violation         | xx (xx.x%)   | xx (xx.x%)                                     | xx (xx.x%)      |
| Patient's decision               | xx (xx.x%)   | xx (xx.x%)                                     | xx (xx.x%)      |
| Withdrawal of consent            | xx (xx.x%)   | xx (xx.x%)                                     | xx (xx.x%)      |
| Etc                              |  |  |                 |

The denominator for each percentage is the number of patients in the column. Completed defined as performed follow-up visit.

Source: Listing 16.2.2

Path\Filename

Page x/y

ABX464-102

ddMMMyyyy HH:MM

Table 14.1.3 Demographic, Baseline and Disease Characteristics (OC Set)

|                                  |                    | 50mg ABX464 (101) +
50mg ABX464 (102)
(N=xx) | Placebo (101) +
50mg ABX464 (102)
(N=xx) | Total
(N=xx) |
|----------------------------------|--------------------|--|--|-----------------|
| Age (years)                      | n                  | xx   | xx   | xx              |
|                                  | Mean               | xx.xx  | xx.xx  | xx.xx           |
|                                  | SD                 | xx.xx  | xx.xx  | xx.xx           |
|                                  | Median             | xx.xx  | xx.xx  | xx.xx           |
|                                  | Minimum            | xx.x   | xx.x   | xx.x            |
|                                  | Maximum            | xx.x   | xx.x   | xx.x            |
| Gender                           | n                  | xx   | xx   | xx              |
|                                  | Male               | xx (xx.x%)   | xx (xx.x%)                                     | xx (xx.x%)      |
|                                  | Female             | xx (xx.x%)   | xx (xx.x%)                                     | xx (xx.x%)      |
| Childbearing*                    | Yes                | xx (xx.x%)   | xx (xx.x%)                                     | xx (xx.x%)      |
|                                  | No                 | xx (xx.x%)   | xx (xx.x%)                                     | xx (xx.x%)      |
| Reason for non-
Childbearing* | Post-menopausal    | xx (xx.x%)   | xx (xx.x%)                                     | xx (xx.x%)      |

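### Table 14.1.2 defines Completed by a follow-up visit, so patients rolling over to ABX464-108 at M48 are not counted and early discontinuers who attend End of Study are

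*SAP*

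**What the plan says.** **SAP.** The footnote to Table 14.1.2 (section 15) gives the only rule: "Completed defined as performed follow-up visit". The table sets Completed against Early withdrawal and lists withdrawal reasons beneath. Its stated source, Listing 16.2.2, has a yes/no field for study completion and a column for the reason if not completed. SAP 5.1 does not define completion, and SAP 1.2 lists no change from the protocol on this point. SAP 11.1 asks for the number of withdrawn patients and their main reason.

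**Protocol, M48 and EoS.** Section 5.2.5 states: "Visit M48 is the last visit in this study before entering the long-term follow-up study ABX464-108". Its procedure list makes the later visit conditional: "Schedule the EoS visit (if patient doesn't enter the study ABX464-108". For early stoppers, section 5.2.6 states: "In case of premature discontinuation occurring during the treatment phase the above examinations should be performed as an End of Study Visit". Section 7.1 adds: "The subjects exiting the study must perform the Follow-up and End of Study (EoS) visits 4 weeks after last study drug intake".

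**Protocol, completion.** Section 7.2 says that patients ineligible for ABX464-108, or unwilling to enter it, are "not considered as prematurely discontinued as they have completed the scheduled treatment of ABX464-102 study". Section 7.3 states: "All subjects, regardless of the completion or premature discontinuation, should perform the Follow-up and End of Study Visits according to the study flow-chart". Section 9.1.3 asks for discontinued patients to be tabulated with their reasons.

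**The concern.** A definition of completion has to separate patients who finished the planned course from those who stopped early. Attendance at a post-treatment visit does not do so here. Some completers are never scheduled for that visit, and early discontinuers are told to attend it. The footnote can therefore err in both directions in the same table.

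The study's primary objective is long-term safety over 48 months, so retention and the reasons for stopping are basic context for the results. With 22 patients, each misclassification in one direction moves the completion rate by 1/22 = 4.5 percentage points. Errors in opposite directions can also cancel, leaving a plausible rate built on the wrong patients.

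**Working it through.** The documents give no completion figure to reproduce, so the check is of the definition against the visit schedule, followed by an illustrative count.

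**Step 1: which visit is meant.** The SAP does not define the follow-up visit. The protocol flow chart (5.1), SAP 3.4 and SAP 16.1 show one visit after treatment stops: EoS, at 28 days. SAP 3.4 also links follow-up to the four weeks after treatment stop. EoS is the workable reading.

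**Step 2: each patient path against the footnote.**

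| Patient | EoS in this study | Footnote | Planned treatment finished |
|---|---|---|---|
| Finishes 48 months, enters ABX464-108 | Not scheduled (Protocol 5.2.5) | Not Completed | Yes |
| Finishes 48 months, does not enter, attends EoS | Scheduled | Completed | Yes |
| Stops early, attends EoS | Required (Protocol 5.2.6, 7.1) | Completed | No |
| Stops early, does not attend EoS | Missed | Not Completed | No |

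Rows 1 and 3 are misclassified. Not every early discontinuer will fall in row 3. Protocol 1.3 reports one patient lost to follow-up, and after a pregnancy Protocol 8.4.2 says "All appropriate withdrawal assessments may be performed at the discretion of the investigator".

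**Step 3: inputs for the illustration.**
- N = 22 enrolled (Protocol 1.3).
- c = patients reaching M48. Assumed 14, using as a proxy the 14 patients treated for more than three years in this study (Protocol 1.2.5). The alternative, 12, is an assumption.
- r = roll-overs to ABX464-108. Not in the documents, so varied from 0 to c.
- a = early discontinuers attending EoS. Not in the documents. At most N − c − 1, allowing for the patient lost to follow-up.
- All M48 completers who do not roll over are assumed to attend EoS.

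**Step 4: formulas.**
- Completed under the footnote = (c − r) + a
- Completed by planned treatment = c
- Misclassified = r + a
- Reasons leaving the table, if Early withdrawal is the complement of Completed = a

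**Step 5: results.**

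| c | a | r | Footnote Completed | Treatment-based | Misclassified |
|---|---|---|---|---|---|
| 14 | 7 | 0 | (14−0)+7 = 21/22 (95.5%) | 14/22 (63.6%) | 7 |
| 14 | 7 | 7 | (14−7)+7 = 14/22 (63.6%) | 14/22 (63.6%) | 14 |
| 14 | 7 | 14 | (14−14)+7 = 7/22 (31.8%) | 14/22 (63.6%) | 21 |
| 14 | 4 | 0 | (14−0)+4 = 18/22 (81.8%) | 14/22 (63.6%) | 4 |
| 14 | 4 | 7 | (14−7)+4 = 11/22 (50.0%) | 14/22 (63.6%) | 11 |
| 14 | 4 | 14 | (14−14)+4 = 4/22 (18.2%) | 14/22 (63.6%) | 18 |
| 12 | 9 | 0 | (12−0)+9 = 21/22 (95.5%) | 12/22 (54.5%) | 9 |
| 12 | 9 | 6 | (12−6)+9 = 15/22 (68.2%) | 12/22 (54.5%) | 15 |
| 12 | 9 | 12 | (12−12)+9 = 9/22 (40.9%) | 12/22 (54.5%) | 21 |

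In the second row the rate is right and 14 of 22 patients are in the wrong category. In the third row every patient counted as Completed is an early discontinuer.

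**The case against.** **The listing may protect the table.** Listing 16.2.2 has its own completion field. If the table is programmed from it, the counts may be right and only the footnote wrong. This is possible, but the SAP does not say whether field or footnote governs. SAP 15 lets programmers change layouts, which is not permission to change a definition.

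**Reasons need not drop out.** The footnote does not say that Early withdrawal means not Completed, so an early discontinuer who attends EoS could appear in both rows. That is a fair reading. However, the shell presents the two as alternatives, and the listing asks for a reason only when the study was not completed. Overlapping rows would be a fault too.

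**Protocol 7.3 may require the visit of everyone.** It does so by reference to the flow chart, and 5.2.5 is the specific rule for roll-overs. If 7.3 is taken literally, the visit is expected of completers and discontinuers alike and still cannot tell them apart.

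**The protocol does not define completion for roll-overs.** This stands in part. Protocol 7.2 names only patients who do not enter ABX464-108, although its reasoning (planned treatment finished) applies equally to those who do. Protocol 9.1.3 and SAP 11.1 ask for withdrawals and reasons without defining completion. Requiring EoS for study completion would also be defensible for patients who do not roll over, and the documents do not settle that choice.

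**The counts are assumed.** They are, and they show direction and possible size only.

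**Conclusion.** The concern holds. The footnote is the SAP's only definition of Completed. Applied to the protocol's visit schedule, it leaves out patients who roll over and counts early discontinuers who attend EoS. This rests on reading the follow-up visit as EoS, the only candidate in either schedule. It does not depend on how Protocol 7.3 is read.

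The true size is unknown, because M48, roll-over and EoS counts are not given. Under the assumptions above, the footnote's completion rate runs from 18.2% to 95.5%, against 63.6% or 54.5% by planned treatment. If the listing field is used instead, the error is confined to the footnote text.

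The consequence is limited to disposition reporting. The primary count of treatment-emergent adverse events and the LOCF and non-responder rules do not use this flag. Individual reasons remain in Listing 16.2.2, and discontinuations for adverse events remain in Tables 14.3.1.4 and 14.3.2.3.

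**What to change.** Before database lock, replace the Table 14.1.2 footnote with: *Completed is defined as having completed the scheduled 48-month treatment and the M48 visit, whether or not the patient enters ABX464-108.* Derive Early withdrawal and its reasons as not Completed under that definition, and state that the completion field in Listing 16.2.2 follows the same rule. EoS attendance and roll-over to ABX464-108 can be shown as separate optional rows, which keeps the safety-visit information without making it the test of completion.

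The cost is one footnote and its derivation. Visit dates and last-dose dates are already listed (Listings 16.2.1 and 16.2.2). The optional roll-over row may need ABX464-108 records, since neither document shows a roll-over field in this study.

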## Clinical Remission

Visit

n

xx

xx

xx

Yes

xx (xx.x%)

xx (xx.x%)

xx (xx.x%)

No

xx (xx.x%)

xx (xx.x%)

xx (xx.x%)

Missing

xx (xx.x%)

xx (xx.x%)

xx (xx.x%)

Etc

## Clinical Response

Visit

n

xx

xx

xx

Etc

xx (xx.x%)

xx (xx.x%)

xx (xx.x%)

Etc

## Clinical Response

Etc

The denominator for each percentage is the number of patients within the column.

Source: Listing 16.2.6.1

Path\Filename

*Programming Note: Please present subgroups in the following order:*

Version Date 20 MAY 2021

Template STATt004

Page 47 of 97

- *All patients*
- *Patients being in clinical response at Baseline Open-Label Study (BOLS)*
- *Patients not being in clinical response at Baseline Open-Label Study (BOLS)*
- *Patients previously treated with biological drugs*
- *Patients naive from biological drugs*

Page x/y

This layout also applies to:

*Table 14.2.5.2 Proportion of Patients: Clinical Remission, Corticosteroid-free Clinical Remission and Clinical Response (NRI Set)*

ABX464-102

ddMMMyyyy HH:MM

Table 14.2.5.3 Shift Table: Clinical Remission (OC Set)

<Subgroup>

|                           |            | 50mg ABX464 (101) +
50mg ABX464 (102)
(N=xx) | Placebo (101) +
50mg ABX464 (102)
(N=xx) | Total      |
|---------------------------|------------|--|--|------------|
| BIS                       | Yes        | xx (xx.x%)   | xx (xx.x%)                                     | xx (xx.x%) |
|                           | No         | xx (xx.x%)   | xx (xx.x%)                                     | xx (xx.x%) |
| BOLS                      | Yes        | xx (xx.x%)   | xx (xx.x%)                                     | xx (xx.x%) |
|                           | No         | xx (xx.x%)   | xx (xx.x%)                                     | xx (xx.x%) |
| Change from BIS to BOLS   | Yes -> Yes | xx (xx.x%)   | xx (xx.x%)                                     | xx (xx.x%) |
|                           | Yes -> No  | xx (xx.x%)   | xx (xx.x%)                                     | xx (xx.x%) |
|                           | Etc        |  |  |            |
| Visit                     | Yes        | xx (xx.x%)   | xx (xx.x%)                                     | xx (xx.x%) |
|                           | No         | xx (xx.x%)   | xx (xx.x%)                                     | xx (xx.x%) |
| Change from BIS to Visit  | Yes -> Yes | xx (xx.x%)   | xx (xx.x%)                                     | xx (xx.x%) |
|                           | Yes -> No  | xx (xx.x%)   | xx (xx.x%)                                     | xx (xx.x%) |
|                           | Etc        |  |  |            |
| Change from BOLS to Visit | Yes -> Yes | xx (xx.x%)   | xx (xx.x%)                                     | xx (xx.x%) |
|                           | Yes -> No  | xx (xx.x%)   | xx (xx.x%)                                     | xx (xx.x%) |
|                           | Etc        |  |  |            |
| Etc                       |            |  |  |            |

The denominator for each percentage is the number of non-missing observations within the column.

BIS: Day 0 of ABX464-101 study

---

BOLS: Day 56 of ABX464-101 study

---

Source: Listing 16.2.6.1

Path\Filename

Page x/y

*Programming Note: Please present subgroups in the following order:*

- All patients
- Patients being in clinical response at Baseline Open-Label Study (BOLS)
- Patients not being in clinical response at Baseline Open-Label Study (BOLS)
- Patients previously treated with biological drugs
- Patients naive from biological drugs

*This layout also applies to:*

*Table 14.2.5.4 Shift Table: Clinical Remission (NRI Set)*

ABX464-102

ddMMMyyyy HH:MM

Table 14.2.6.1 Proportion of Patients: Endoscopic Improvement and Endoscopic Remission (OC Set)

<Subgroup>

|  | 50mg ABX464 (101) +
50mg ABX464 (102)
(N=xx) | Placebo (101) +
50mg ABX464 (102)
(N=xx) | Total
(N=xx) |
|--|--|--|-----------------|
|--|--|--|-----------------|

## Endoscopic Improvement

| Visit   | n | xx         | xx         | xx         |
|---------|---|------------|------------|------------|
| Yes     |   | xx (xx.x%) | xx (xx.x%) | xx (xx.x%) |
| No      |   | xx (xx.x%) | xx (xx.x%) | xx (xx.x%) |
| Missing |   | xx (xx.x%) | xx (xx.x%) | xx (xx.x%) |

Etc

## Endoscopic Remission

| Visit   | n | xx         | xx         | xx         |
|---------|---|------------|------------|------------|
| Yes     |   | xx (xx.x%) | xx (xx.x%) | xx (xx.x%) |
| No      |   | xx (xx.x%) | xx (xx.x%) | xx (xx.x%) |
| Missing |   | xx (xx.x%) | xx (xx.x%) | xx (xx.x%) |

Etc

The denominator for each percentage is the number of patients within the column.

Endoscopic Improvement and Endoscopic Remission are based on central reading endoscopy.

Source: Listing 16.2.6.1

Path\Filename

Page x/y

Programming Note: Please present subgroups in the following order:

- All patients

Version Date 20 MAY 2021

Template STATt004

Page 51 of 97

- *Patients being in clinical response at Baseline Open-Label Study (BOLS)*
- *Patients not being in clinical response at Baseline Open-Label Study (BOLS)*
- *Patients previously treated with biological drugs*
- *Patients naive from biological drugs*

This layout also applies to:

*Table 14.2.6.2 Proportion of Patients: Endoscopic Improvement and Endoscopic Remission (NRI Set)*

*Table 14.2.7.1 Proportion of Patients: Sustained clinical remission and sustained endoscopic remission/improvement (OC Set)*

*Table 14.2.7.2 Proportion of Patients: Sustained clinical remission and sustained endoscopic remission/improvement (NRI Set)*

ABX464-102

ddMMMyyyy HH:MM

Period X

Table 14.3.1.1 Adverse Events (OC Set)

|  | 50mg ABX464 (101) + | Placebo (101) +   | Total
(N=xx) |
|--|---------------------|-------------------|-----------------|
|  | 50mg ABX464 (102)   | 50mg ABX464 (102) |                 |
|  | (N=xx)              | (N=xx)            |                 |
|  | E n (%)             | E n (%)           | E n (%)         |
| Any Adverse Event  | xx xx (xx.x%)       | xx xx (xx.x%)     | xx xx (xx.x%)   |
| Any Treatment-Emergent Adverse Event                     | xx xx (xx.x%)       | xx xx (xx.x%)     | xx xx (xx.x%)   |
| Any Serious Adverse Event                                | xx xx (xx.x%)       | xx xx (xx.x%)     | xx xx (xx.x%)   |
| Any Severe Adverse Event                                 | xx xx (xx.x%)       | xx xx (xx.x%)     | xx xx (xx.x%)   |
| Any Adverse Event leading to death                       | xx xx (xx.x%)       | xx xx (xx.x%)     | xx xx (xx.x%)   |
| Any Treatment-Emergent Adverse Event of Special Interest | xx xx (xx.x%)       | xx xx (xx.x%)     | xx xx (xx.x%)   |

The table presents number of events (E) and number and percentage of patients (n(%)).

The denominator for each percentage is the number of patients within the column.

MedDRA version <XX.X>.

Period 1: Any adverse event which occurs or worsens from first dosing to the last dosing day. Period 2: Any adverse event which occurs after the last dosing day.

Source: Listing 16.2.7

Path\Filename

Page x/y

*Programming Note: Please present for both periods with the number of the period in the header (Period X).*

*This layout also applies to:*

*Table 14.3.1.4 Treatment-Emergent Adverse Events Leading to Investigational Product Discontinuation (OC Set)*

*Table 14.3.1.5 Treatment-Emergent Adverse Events (OC Set)*

Version Date 20 MAY 2021

Template STATt004

Page 53 of 97

*Table 14.3.1.7 Serious Treatment-Emergent Adverse Events (OC Set)*  
*Table 14.3.1.9 Treatment-Emergent Adverse Events of Special Interest (OC Set)*

ABX464-102

ddMMMyyyy HH:MM

Period X

Table 14.3.1.2 Adverse Events by Severity (OC Set)

| Severity           | 50mg ABX464 (101) +           | Placebo (101) +                                 | Total
(N=xx)                                 |
|--------------------|-------------------------------|---|---|
|                    | 50mg ABX464 (102)             | 50mg ABX464 (102)                               |   |
|                    | (N=xx)                        | (N=xx)  |   |
| E                  | n (%)                         | E   | n (%)   |
| Any Adverse Events | xx xx (xx.x%)                 | xx xx (xx.x%)                                   | xx xx (xx.x%)                                   |
| SOC                | Grade 1
Grade 3            | xx xx (xx.x%)
xx xx (xx.x%)                  | xx xx (xx.x%)
xx xx (xx.x%)                  |
| PT                 | Grade 1
Grade 1
Grade 3 | xx xx (xx.x%)
xx xx (xx.x%)
xx xx (xx.x%) | xx xx (xx.x%)
xx xx (xx.x%)
xx xx (xx.x%) |
| Etc                |                               |   |   |
| Etc                |                               |   |   |

The table presents number of events (E) and number and percentage of patients (n(%)).

The denominator for each percentage is the number of patients within the column.

MedDRA version <XX.X>.

Period 1: Any adverse event which occurs or worsens from first dosing to the last dosing day. Period 2: Any adverse event which occurs after the last dosing day.

Source: Listing 16.2.7

Path\filename

Page x/y

*Programming Note: Please present for both periods with the number of the period in the header (Period X). Only present severity categories with at least 1 non-missing value.*

*This layout also applies to:*

*Table 14.3.1.6 Treatment-Emergent Adverse Events by Severity (OC Set)*

Version Date 20 MAY 2021

Template STATt004

Page 55 of 97

ABX464-102

ddMMMyyyy HH:MM

Period X

Table 14.3.1.3 Treatment-Emergent Adverse Events by Relationship to Study Drug (OC Set)

| Relationship to Study Drug | 50mg ABX464 (101) + |               | Placebo (101) +   |               | Total
(N=xx) |  |
|----------------------------|---------------------|---------------|-------------------|---------------|-----------------|--|
|                            | 50mg ABX464 (102)   |               | 50mg ABX464 (102) |               |                 |  |
|                            | (N=xx)              | (N=xx)        | (N=xx)            | (N=xx)        |                 |  |
| E                          | n (%)               | E             | n (%)             | E             | n (%)           |  |
| Any Adverse Event          | xx xx (xx.x%)       |               | xx xx (xx.x%)     |               | xx xx (xx.x%)   |  |
| SOC                        | Not related         | xx xx (xx.x%) |                   | xx xx (xx.x%) | xx xx (xx.x%)   |  |
|                            | Related             | xx xx (xx.x%) |                   | xx xx (xx.x%) | xx xx (xx.x%)   |  |
| PT                         | Related             | xx xx (xx.x%) |                   | xx xx (xx.x%) | xx xx (xx.x%)   |  |
| PT                         | Not related         | xx xx (xx.x%) |                   | xx xx (xx.x%) | xx xx (xx.x%)   |  |
|                            | Related             | xx xx (xx.x%) |                   | xx xx (xx.x%) | xx xx (xx.x%)   |  |
| Etc                        |                     |               |                   |               |                 |  |
| Etc                        |                     |               |                   |               |                 |  |

The table presents number of events (E) and number and percentage of patients (n(%)).

The denominator for each percentage is the number of patients within the column.

MedDRA version <XX.X>.

Period 1: Any adverse event which occurs or worsens from first dosing to the last dosing day. Period 2: Any adverse event which occurs after the last dosing day.

Source: Listing 16.2.7

Path\Filename

Page x/y

Version Date 20 MAY 2021

Template STATt004

Page 56 of 97

*Programming Note: Please present for both periods with the number of the period in the header (Period X). Only present categories with at least 1 non-missing value.*

This layout also applies to:

*Table 14.3.1.8 Severe TEAEs (grade 3 and 4) by relationship to study drug (OC Set)*

ABX464-102

ddMMMyyyy HH:MM

Table 14.3.2.1 Listing of Deaths (OC Set)

| Treatment | Centre/ Patient number | Date of death   | Cause of death       | Period             |
|-----------|------------------------|-----------------|----------------------|--------------------|
| xxxxxx    | xxxx-xxx               | ddMMMyyyy HH:MM | xxxxxxxxxxxxxxxxxxxx | Period 1/ Period 2 |
| xxxxxx    | xxxx-xxx               | ddMMMyyyy HH:MM | xxxxxxxxxxxxxxxxxxxx | Period 1/ Period 2 |
| Etc       |                        |                 |                      |                    |

Path\Filename

Page x/y

ABX464-102

ddMMMyyyy HH:MM

Table 14.3.2.2 Listing of Serious Adverse Events (OC Set)

| Treatment   | Centre/
Patient
number | Adverse Event
PT            | Onset date         | Resolution
date / ongoing    | Outcome  | Relationship to
study drug | Action taken with
study drug            | Other action
taken   | Period                |
|---|------------------------------|--------------------------------|--------------------|---------------------------------|--|-------------------------------|--|---|-----------------------|
| xxxxx   | xxxx-xxx                     | xxxxxxxxxx
xxxxxxxx
xxxx | ddMMMyyyy
HH:MM | ddMMMyyyy
HH:MM /
ongoing | Resolved/
Resolved
without
sequelae/
Etc | Related/ Not
related       | None/ Temporary
discontinuation/
Etc | Concomitant
medication
(CM no.)/
Procedure (PR
no.) | Period 1/
Period 2 |
| Etc   |                              |                                |                    |                                 |  |                               |  |   |                       |
| Etc   |                              |                                |                    |                                 |  |                               |  |   |                       |
| 
MedDRA version <XX.X>.
 
Period 1: Any adverse event which occurs or worsens from first dosing to the last dosing day. Period 2: Any adverse event which occurs after the last dosing day .
 |                              |                                |                    |                                 |  |                               |  |   |                       |
| Path\Filename   |                              |                                |                    |                                 |  |                               |  |   |                       |
| Page x/y  |                              |                                |                    |                                 |  |                               |  |   |                       |

*This layout also applies to:*

Table 14.3.2.3 Listing of Adverse Events Leading to Withdrawals (OC Set)

ABX464-102

ddMMMyyyy HH:MM

Table 14.3.3.1 Change from Baseline of Laboratory Parameters: Hematology (OC Set)

|                               |         | 50mg ABX464 (101) +
50mg ABX464 (102)
(N=xx) | Placebo (101) +
50mg ABX464 (102)
(N=xx) | Total
(N=xx) |
|-------------------------------|---------|--|--|-----------------|
| Parameter              |         |  |  |                 |
| Baseline                      | n       | xx   | xx   | xx              |
|                               | Mean    | xx.xx  | xx.xx  | xx.xx           |
|                               | SD      | xx.xx  | xx.xx  | xx.xx           |
|                               | SEM     | xx.xx  | xx.xx  | xx.xx           |
|                               | Median  | xx.xx  | xx.xx  | xx.xx           |
|                               | Minimum | xx.x   | xx.x   | xx.x            |
|                               | Maximum | xx.x   | xx.x   | xx.x            |
| Visit                         | n       | Xx   | Xx   | Xx              |
|                               | Mean    | xx.xx  | xx.xx  | xx.xx           |
|                               | Etc     |  |  |                 |
| Change from Baseline to Visit | n       | Xx   | Xx   | Xx              |
|                               | Mean    | xx.xx  | xx.xx  | xx.xx           |
|                               | Etc     |  |  |                 |
| Etc                           |         |  |  |                 |
| Etc                           |         |  |  |                 |

Source: Listing 16.2.8.1  
Path\Filename

Version Date 20 MAY 2021

Template STATt004

Page 60 of 97

*Programming Note: start each parameter on a new page*

*This layout also applies to:*

*Table 14.3.3.2 Change from Baseline of Laboratory Parameters: Biochemistry (OC Set) [Source: Listing 16.2.8.2]*

ABX464-102

ddMMMyyyy HH:MM

Table 14.3.3.3 Shift Table of Laboratory Parameters: Hematology (OC Set)

|  | 50mg ABX464 (101) +
50mg ABX464 (102)
(N=xx) | Placebo (101) +
50mg ABX464 (102)
(N=xx) | Total
(N=xx) |
|--|--|--|-----------------|
|--|--|--|-----------------|

